8.8.4. Banked Biospecimens for Biomarkers

Banked biospecimens for biomarkers are not included in this study.

8.9. Immunogenicity Assessments

Immunogenicity assessments are not applicable in this study.

8.10. Health Economics

Not applicable: Health economic/medical resource utilization parameters are not evaluated in this study.

9. STATISTICAL CONSIDERATIONS

Detailed methodology for summary and statistical analyses of the data collected in this study is outlined here and further detailed in the SAP, which will be maintained by the sponsor. The SAP may modify what is outlined in the protocol where appropriate; however, any major modifications of the primary endpoint definitions or their analyses will also be reflected in a protocol amendment.

9.1. Estimands and Statistical Hypotheses

For the primary safety endpoint, there is no formal hypothesis testing. The analyses will focus on estimation. Summary statistics for each group with 95% confidence intervals will be provided.

Estimands

Not applicable since there is no formal statistical hypothesis testing for this study.

9.2. Sample Size Determination

Approximately 60 adults 18 to 50 years of age will be randomized in a 1:1 allocation ratio to either the PF-06651600 200 mg QD/50 mg QD dose group or the placebo group.

For the primary safety endpoint, change from baseline in I-V interwave latency on BAEP at Month 9, the published standard deviations for I-V interwave latency on BAEP range from 0.1 to 0.3 ms. Assuming the standard deviation of 0.2 ms, and assuming standard deviation of change from baseline is similar as the standard deviation of actual score, the half-width of 95% confidence interval for the group will be 0.07 ms for 30 participants per group.

9.3. Analysis Sets

For purposes of analysis, the following populations are defined:

Population	Description
Efficacy	All randomized participants taking at least 1 dose of study intervention. Data will be summarized according to the intervention they were assigned.
Safety	All participants taking at least 1 dose of study intervention. Participants will be analyzed according to the intervention they actually received.

9.4. Statistical Analyses

The statistical analysis plan will be developed and finalized before database lock and will describe the participant populations to be included in the analyses, and procedures for accounting for missing, unused, and spurious data. This section is a summary of the planned statistical analyses of the primary, the secondary, and the exploratory endpoints.

9.4.1. Timing of the Analyses

There will be 3 Clinical Study Reports (CSRs) for this study: one PCD-CSR, and two supplemental CSRs.

The PCD-CSR will include the primary analysis for this study, which will be conducted following the PCD at Month 9 (TP1) (Section 4.4), and after the Month 9 data are cleaned and locked for all participants. The following data will be included:

- Efficacy data through Month 9 (TP1)
- All safety data collected through the PCD data cut-off date

The supplemental CSR 1 will be prepared after the last participant completes the 4-week follow-up visit, or the Month 15E visit (TP2) if the last participant is enrolling in TP3. This CSR will include:

- Efficacy through Month 15E (TP1+TP2)
- All safety data collected through the cut-off date for this CSR.

The supplemental CSR 2 will be focused on safety and efficacy data from TP3 and will be prepared after the last participant completes the last visit or discontinues from the study.

9.4.2. Efficacy Analyses

Efficacy data will be summarized by the treatment assignment based on efficacy population. The baseline is defined as the last measurement before the first dose in the placebo-controlled phase.

The secondary endpoints for SALT include both the overall SALT and AA SALT scores. The overall SALT score includes hair loss regardless of etiology (ie, scalp hair loss due to both non-AA and AA). The non-AA SALT score only takes into account scalp hair loss other than that due to AA and is required to be assessed only at:

- Month 9 (end of TP1) (or Month 6 for those participants, who enter the active therapy extension phase at Month 6),
- Month 15E (end of TP2) or Early Termination visit (as appropriate), and
- Month 51E (end of TP3) or Early Termination visit (as appropriate).

The AA SALT score at each visit will be calculated using non-AA SALT scores as follows:

- the non-AA SALT score collected at Month 9 (or Month 6) or the Early Termination visit (as appropriate) will be used for visits in TP1.

- the non-AA SALT score collected at Month 15E or the Early Termination visit (as appropriate) will be used for visits in TP2, and
- the non-AA SALT score collected at Month 51E or the Early Termination visit (as appropriate) will be used for visits in TP3.
- The formula for deriving the AA SALT score is given by: AA SALT score = overall SALT score – non-AA SALT score.

PCD CSR (Month 9; TP1)	
Endpoint	Statistical Analysis Methods
Primary	
 • There are no primary efficacy endpoints.
Secondary	
 • For PGI-C response, for the placebo-controlled phase, number and percentage with 95% confidence interval (based on Clopper-Pearson method) by treatment group, and treatment difference with 95% confidence interval (based on Chan and Zhang's exact method⁽⁵⁶⁾) will be presented. Participants who discontinue from the study for any reason or who switch to active therapy extension phase before Month 9 will be considered as non-responders. • In the placebo-controlled phase, change from baseline in overall and AA SALT score will be analyzed using linear mixed-effects model with baseline, treatment group, visit and treatment group by visit interaction as fixed effects, and participant as a random effect with unstructured covariance matrix assumption. The estimated mean, mean difference, with 95% confidence interval based on the model will be presented at each time point.
Exploratory	
 • There are no exploratory efficacy endpoints included in this CSR

Supplementary CSR 1 (Month 15E; TP2)	
Endpoint	Statistical Analysis Methods
Primary	
 • There are no primary efficacy endpoints.
Secondary	
 • For PGI-C response in the active therapy extension phase, number, and percentage with 95% confidence interval (based on Clopper-Pearson method) by initial treatment group will be presented based on observed data. • For overall and AA SALT score in the active therapy extension phase, descriptive statistics will be presented by initial treatment group. Observed data will be used.
Exploratory	
 • There are no exploratory efficacy endpoints included in this CSR.

Supplementary CSR 2 (Month 51E; TP3)	
Endpoint	Statistical Analysis Methods
Primary	
 • There are no primary efficacy endpoints.
Secondary	
 • There are no secondary efficacy endpoints included in this CSR.

Supplementary CSR 2 (Month 51E; TP3)	
Endpoint	Statistical Analysis Methods
Exploratory	
 For PGI-C response in TP3, number, and percentage with 95% confidence interval (based on Clopper–Pearson method) by initial treatment group will be presented based on observed data. For overall and AA SALT score in TP3, descriptive statistics will be presented by initial treatment group. Observed data will be used.

9.4.3. Safety Analyses

The safety analyses will be summarized by initial treatment group in the safety population based on observed data. The baseline is defined as the last measurement before the first dose in the placebo-controlled phase.

All standard safety summary such as the incidence of safety events will be summarized by the initial treatment group for the placebo-control phase, the active therapy extension phase and TP3 extension phase. For initial active group, the overall summary for the whole study duration will also be provided.

PCD CSR (Month 9; TP1)	
Endpoint	Statistical Analysis Methods
Primary	
 The primary endpoint is change from baseline in I-V interwave latency on BAEP at Month 9. It will be analyzed using linear mixed-effects model with baseline, treatment group, visit (Months 6 and 9) and treatment group by visit interaction as fixed effects, and subject as a random effect with unstructured covariance matrix assumption. For participants who switch to the active therapy extension phase at Month 6, only their data through Month 6 will be included in the analysis of the placebo-controlled period. The estimated means, with their standard errors and 95% confidence intervals based on the model will be presented.
Secondary	
 Change from baseline in I-V interwave latency on BAEP during the placebo-controlled phase will be analyzed using linear mixed-effects model with baseline, treatment group, visit (Months 6 and 9) and treatment group by visit interaction as fixed effects, and participant as a random effect with unstructured covariance matrix assumption. The estimated means, with their standard errors and 95% confidence intervals based on the model will be presented. For data in the active therapy extension phase, descriptive statistics will be presented. For change from baseline in IENFD at Month 9 and Month 15E and change from baseline in axonal dystrophy in skin punch biopsies at Month 9 and Month 15E: descriptive statistics will be presented. Change and percent change from baseline in amplitude of wave V: the same method linear mixed-effect model as

PCD CSR (Month 9; TP1)	
Endpoint	Statistical Analysis Methods
	
the I-V interwave latency will be used for Month 6 and Month 9 data. For data in the active therapy extension phase, descriptive statistics will be presented.
 
 • Absence of wave V on BAEP will be summarized descriptively using number and percentage of participants by treatment group at each intensity level. • The incidence rates of safety events, significant clinical abnormalities, vital signs and ECG will be summarized descriptively using number and percentage.

Supplementary CSR 1 (Month 15E; TP2)	
Endpoint	Statistical Analysis Methods
Primary	
 • There are no primary safety endpoints included in the supplemental CSR 1.
Secondary	
 • For change from baseline in I-V interwave latency on BAEP: descriptive statistics will be presented. • For change from baseline in IENFD at Month 9 and Month 15E and change from baseline in axonal dystrophy in skin punch biopsies at Month 9 and Month 15E: descriptive statistics will be presented. • Change and percent change from baseline in amplitude of wave V: descriptive statistics will be presented. • Absence of wave V on BAEP will be summarized descriptively using number and percentage of participants by treatment group at each intensity level. • The incidence rates of safety events, significant clinical abnormalities, vital signs and ECG will be summarized descriptively using number and percentage.

Supplementary CSR 2 (Month 51E; TP3)	
Endpoint	Statistical Analysis Methods
Primary	
 • There are no primary safety endpoints included in the supplemental CSR 2.
Secondary	
 • The incidence rates of safety events, significant clinical abnormalities and vital signs in TP3 will be summarized descriptively using number and percentage.

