4. STUDY DESIGN

4.1. Overall Design

Study B7981037 is a Phase 2a, randomized, double-blind, parallel group, placebo-controlled safety study designed to evaluate the safety and tolerability of PF-06651600, including the assessment of BAEP and IENF, in adults with $\geq 25\%$ scalp hair loss due to AA.

Approximately 60 adults 18 to 50 years of age will be randomized 1:1 to receive either PF-06651600 or placebo. If there are issues related to the integrity of some peripheral nerve punch biopsy samples, up to an additional 20 participants may be added at the discretion of the Sponsor to ensure adequate numbers of participants with interpretable biopsies.

Treatment Period 1 (TP1) and Treatment Period 2 (TP2):

The total duration of participation in the study for TP1 and TP2 will be approximately 26 months.

This includes up to a 5-week screening period, a 9-month placebo-controlled treatment phase, a 15-month active therapy extension phase, and a 4-week follow-up period [for participants not continuing to TP3 or discontinuation of study intervention (see Schema Section 1.2)]. Screening will occur within 35 days prior to Day 1 of the study to confirm that selection criteria for the study are met. At Month 9, the placebo-controlled phase will end, and all participants may enter the active therapy extension phase of the study and receive PF-06651600. For any participant discontinued for a neurological or auditory adverse event, the participant will be evaluated again at 6 months after discontinuation; the maximum duration of participation in the study for such participants could be approximately 32 months if the event occurred at the last visit.

At Month 6, any participant with a baseline overall SALT score ≤ 75 will have the option to enter the active therapy extension phase if their overall SALT score at Month 6 has increased from baseline by ≥ 25 points. Those participants who enter the active therapy extension phase at Month 6 are to complete at that visit all the Month 6 (Visit 5) assessments and then follow the schedule of visits in the active therapy extension phase starting with Month 3E skipping the Month 9 (Visit 6).

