BAEPs will be measured at screening and at Months 6, 9, 9E, and 15E, or early termination for all participants. IENF will be assessed at Day 1, Month 9, and Month 15E, or early termination. Participants who enter the active therapy extension phase at Month 6 will have a skin punch biopsy taken at Month 6 for IENF assessments instead of at Month 9. The skin biopsy must be collected before the start of Active Therapy Extension Phase.

Participants who discontinue the study due to a neurological or auditory AE will have assessments performed at the time of discontinuation and repeated at 6 months after the last dose of study intervention (see Section 10.7).

Treatment Period 3 (TP3):

The total duration for TP3 will be of variable length for individual participants; assuming a participant does not require discontinuation per protocol. A participant may continue to receive PF-06651600 in TP3 for a maximum of an additional 36 months or until availability of commercial product in their country, or until the Sponsor terminates the study in that country, whichever occurs first.

In TP3, participants will receive 50 mg QD PF-06651600. The total duration of participation in TP3 is approximately 37 months, including up to 36 months study intervention, and a follow up period of 4 weeks after completion or discontinuation of study intervention (see Section 1.2 Schema).

Observation Period:

If study intervention is permanently discontinued, the participant will be asked to remain in the study after the Follow-up visit without study intervention, and continue to comply with study visit schedules for approximately 2 years after the last dose of study intervention or until study end, whichever occurs first; refer to Section 7.1.1.1 for further details.

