4.3. Justification for Dose

This study will evaluate PF-06651600 administered at a dose of 200 mg QD for 4 weeks followed by a dose of 50 mg QD for up to 60 months for participants proceeding to TP3. This dose regimen was selected as it is the highest dose regimen being evaluated in the Phase 3 development program in AA.

Exposure margins of the proposed clinical doses relative to the nonclinical NOAEL exposures are summarized in Table 1.

Table 1. PF-06651600 Exposure Margins and No Observed Adverse Effects Level

	Dose/Route	Mean AUC in Dogs (unbound, ng•hr/mL)	Mean Clinical AUC (unbound, ng•hr/mL)	Calculated Safety Margin
Safety Exposure Margins for Human 200 mg QD Dose in AA patients				
Dog 2-month toxicology (Study 1)	NOAEL: 45 mg/kg oral	44100	5310	8.3
Dog 9-month toxicology (Study 2)	NOAEL: 10 mg/kg oral	7940	5310	1.5
Safety Exposure Margins for Human 50 mg QD Dose in AA patients				
Dog 2-month toxicology (Study 1)	NOAEL: 45 mg/kg oral	44100	1070	41
Dog 9-month toxicology (Study 2)	NOAEL: 10 mg/kg oral	7940	1070	7.4

Abbreviations: AUC = area under the concentration-time curve; NOAEL = no observed adverse effect level; QD = once daily.

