#### **6.2.6. Incidence of Treatment-emergent Adverse Events (TEAEs)**

- **Endpoint:** Incidence of subjects with treatment emergent adverse events.
- **Population:** Safety.
- **Statistical Method:** Descriptive statistics with number and percentage of subjects with the events only.

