#### **6.7. Safety Summaries and Analyses**

Safety analysis will be based on the safety population.

Analyses for the primary and secondary safety endpoints are discussed in [Section 6.1](#) and [Section 6.2](#).

In general, safety data will be presented in tabular and/or graphical format and summarized descriptively, where appropriate. All safety endpoints will be listed and summarized in accordance with Pfizer Standards. Categorical outcomes (eg, AEs) will be summarized by subject counts and percentage. Continuous outcome (eg, blood pressure, pulse rate, etc.) will be summarized using N, mean, median, standard deviation, etc. Change from baseline in laboratory data, ECGs and vital signs will also be summarized. Subject listings will be produced for these safety endpoints accordingly. Clinically significant abnormalities in vital signs and clinical laboratory values are discussed in [Sections 6.2.9](#) and [6.2.10](#).

In order to report the impact of COVID-19 on clinical trial populations and study data, additional listings and summaries will be produced:

- Protocol deviations related to COVID-19
- Summary of discontinuations due to COVID-19 related reasons
- Discontinuation from study/study drug interruptions due to COVID-19 related adverse events
- COVID-19 related adverse events
- Number of days with missed doses due to COVID-19
- Missed visits summary for I-V interval latency on BAEP

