**Table 4. Groups**

Period	Groups
Placebo-controlled phase (TP1)	
 
• Ritlecitinib 200/50 mg QD
 
• Placebo
 

Active therapy extension phase (TP2)	
 
• Ext Ritlecitinib 50 mg QD
 
• Ext Ritlecitinib 200/50mg QD
 

Overall (TP1+TP2+TP3+Observation period)	
 
• Ritlecitinib 200/50/50 mg QD
 
• Any Ritlecitinib
 
• Any Ritlecitinib + Placebo (Total)
 

- For all the other tables, groups will be:
  - Ritlecitinib 200/50/50 mg QD
  - Placebo → Ritlecitinib 200/50 mg QD.

### 8.3. Supplemental CSR 2

The supplemental CSR 2 will be focused on safety and efficacy data from TP3 and will be prepared after the last participant completes the last visit or discontinues from the study.

- Disposition date of TP2 (or of 4 weeks follow-up period if participants didn't enter TP3) will be used to identify records in TP2 and TP3.
- All safety data in TP3, regardless of whether participants are in the Observation Period or not, will be included in summary tables.
- Only one group “All participants” including all participants will be used in all summaries.
- Efficacy data of participants while in the Observation Period will not be included in summary tables that present TP3 data by visit. Instead, listings and plots may be provided.

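### Adverse events are planned only as crude percentages, which are not comparable across treatment periods or in the pooled ritlecitinib columns

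*Protocol*

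**What the plan says.** Protocol 9.4.3, for both the PCD-CSR and supplemental CSR 1, says: "The incidence rates of safety events, significant clinical abnormalities, vital signs and ECG will be summarized descriptively using number and percentage". The supplemental CSR 2 entry is the same in substance, without ECG. SAP section 9 also uses the term incidence rates. The method in SAP 6.2.6, repeated in 6.2.7 and 6.2.8, is "Descriptive statistics with number and percentage of subjects with the events only", and SAP 6.7 says "Categorical outcomes (eg, AEs) will be summarized by subject counts and percentage".

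The columns come from SAP section 8. Tables 3 and 4 list TP1 (ritlecitinib, placebo), TP2 (the two extension groups) and an Overall block containing Ritlecitinib 200/50/50, Any Ritlecitinib, and a total including placebo. In Table 3 the Overall block covers TP1 and TP2. In Table 4 it is labelled "Overall (TP1+TP2+TP3+Observation period".

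Planned durations are in Protocol 4.1: "a 9-month placebo-controlled treatment phase, a 15-month active therapy extension phase", then TP3 "for a maximum of an additional 36 months or until availability of commercial product in their country", or until the sponsor ends the study there. Protocol 9.4.3 also promises: "For initial active group, the overall summary for the whole study duration will also be provided".

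SAP 3.6.1 defines risk periods with start and end dates, and SAP 6.6.3 summarizes duration of treatment. Neither is used as a denominator for adverse events.

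**The concern.** A crude percentage depends on how long people were watched as well as on how often events occur. The only placebo column in these tables covers 9 months. The TP2 columns cover 15 months when complete. Read as on-drug time, Any Ritlecitinib pools initial-active participants with up to 24 months over TP1 and TP2 and former-placebo participants with up to 15.

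Follow-up also varies within columns. At the PCD cut-off, time in TP2 depends on when a participant enrolled. TP3 length depends on country and commercial availability, so even the single CSR 2 group has no fixed time base. The Table 4 Overall block adds Observation Period time, which is off drug and can last about 2 years.

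Protocol 4.2 gives longer-term safety information as the reason for the extension. With percentages alone, a reader cannot separate a change in risk over time from longer follow-up. Calling the percentages incidence rates invites the wrong reading.

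**Working it through.** **Inputs from the documents.** TP1 is 9 months, TP2 15 months and TP3 at most 36 months (Protocol 4.1). There are about 30 participants per group (Protocol 9.2). Columns are those of SAP Tables 3 and 4.

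**Assumptions.** The documents give no planning rate for adverse events and no dropout rate. I take the proportion with an event by 9 months, p9, as 5%, 10% or 20%, with a constant hazard that is the same in every column (no drug effect), and everyone completing TP1 and TP2.

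**Step 1, the plan's own duration.** 9 + 15 + 36 = 60 months, which agrees with Protocol 4.3 ("followed by a dose of 50 mg QD for up to 60 months for participants proceeding to TP3"). Over TP1 and TP2, the initial active group has 9 + 15 = 24 months on drug and the former placebo group has 15.

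**Step 2, percentage by length of follow-up.** p(T) = 1 − (1 − p9)^(T/9), with T in months. For p9 = 10%:
- 15 months: 1 − 0.9^(15/9) = 16.1%
- 24 months: 1 − 0.9^(24/9) = 24.5%
- Any Ritlecitinib, TP1 and TP2: (30 × 24.5% + 30 × 16.1%)/60 = 20.3%

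| p9 (TP1, 9 months) | TP2 (15 months) | Initial active, TP1+TP2 (24 months) | Any Ritlecitinib, TP1+TP2 | Same rate per 100 person-years |
|---|---|---|---|---|
| 5% | 8.2% | 12.8% | 10.5% | 6.84 |
| 10% | 16.1% | 24.5% | 20.3% | 14.05 |
| 20% | 31.1% | 44.8% | 38.0% | 29.75 |

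The last column is −100 × ln(1 − p9)/0.75. It is identical for every column of the table, which is what a reader would want to see when risk has not changed. The Any Ritlecitinib figure is for completed TP1 and TP2. In the PCD-CSR, TP2 is only partly complete, so the inflation there is smaller.

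**Step 3, the randomized contrast.** Protocol 4.1 lets some participants move to active therapy at Month 6. By then p(6) = 1 − 0.9^(6/9) = 6.8%. If k of 30 in an arm switch, the TP1 percentage is [k × 6.8% + (30 − k) × 10%]/30. For k = 3, 6 and 9 this gives 9.7%, 9.4% and 9.0%. The distortion within TP1 is small.

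**Step 4, person-time available.** With no dropout, the maximum is 30 × 9/12 = 22.5 person-years per TP1 arm, 30 × 15/12 = 37.5 per TP2 column, 30 × 24/12 = 60 for the initial active group over TP1 and TP2, and 60 + 37.5 = 97.5 for Any Ritlecitinib.

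**The case against.** A reader might infer that the placebo comparison itself is unsound. The documents do not support that. The two TP1 columns share a planned 9 months, the two TP2 columns share a planned 15, and Step 3 shows that Month 6 switching moves a TP1 percentage very little. Crude percentages are usable for both contrasts, no hypothesis is tested, and the plan does not propose comparing TP1 placebo with later columns. This stands and limits the point.

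Parts of the remedy also exist already. SAP 3.6.1 separates the risk periods and has CSR 2 report TEAEs for the TP3 and Observation risk periods separately. Duration of treatment is tabulated for the same groups as the adverse events, so unequal exposure is visible. Visible exposure does not make the percentages comparable, however, and the CSR 1 Overall block has no such split. SAP 6.7.1 refers to sponsor standards and says adjudicated data are reported separately. Neither method is in these documents, so neither can be assumed to supply a rate.

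The most substantial objection is to the rate itself. A constant hazard is doubtful around the initial 4-week 200 mg period, since Protocol 2.3 reports more of some TEAEs with loading-dose regimens. Suppose 6 of 30 participants have a first event in the first 4 weeks (on average at 2 weeks) and nobody later. The percentage is 20% at both 9 and 24 months. The rate falls from 6/(24 × 0.75 + 0.23) = 33 to 6/(24 × 2 + 0.23) = 12 per 100 person-years, so longer columns would look safer. Precision is also poor: 3 events in 22.5 person-years give 13.3 per 100, with an exact 95% CI of about 3 to 39. Both objections are sound reasons to show a rate beside n (%) and not in its place. They do not justify having no time base.

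**Conclusion.** The point holds for comparisons across periods and for the Overall and Any Ritlecitinib columns. Over completed TP1 and TP2 alone, unequal follow-up roughly doubles the apparent percentage relative to TP1 placebo with no drug effect. This rests on the assumed event proportions, a constant hazard and no dropout; the direction holds whenever new first events continue to occur over time.

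A reader might also infer that the tables set 60-month columns beside 9-month ones. They do not. Table 4 belongs to CSR 1, prepared once the last participant finishes TP2 or its follow-up visit, and CSR 2 uses one group of all participants. Version dates suggest a ceiling for Table 4. The original protocol is dated 8 May 2020, and SAP version 4.0 of 17 August 2022 already refers to the PCD-CSR, 27.3 months later. Enrolment therefore spanned at most about 27.3 − 9 = 18.3 months, and the longest follow-up at the CSR 1 cut is about 18.3 + 24 = 42 months. This assumes no enrolment before the original protocol date and a PCD before that SAP version. Sixty months arises only in the Protocol's whole-study summary for the initial active group, where 10% at 9 months would become 1 − 0.9^(60/9) = 50.5%. The SAP does not carry that summary over, and the two documents need to be reconciled.

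The study is descriptive and no data collection is affected. This is a worthwhile, low-cost improvement, not a flaw in the primary analysis.

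**What to change.** 1. Keep n (%) everywhere.
2. For the TP2, Overall, Any Ritlecitinib and TP3 columns, and for TP1 as reference, add the number of participants with a first event per 100 participant-years at risk, with exact Poisson 95% CIs. Use the SAP 3.6.1 risk periods, censoring at first event or end of risk period.
3. In the CSR 1 Overall columns, show Observation Period events and time separately from on-drug time.
4. Assign the 35 days after last dose to one period only. In SAP 3.6.1 the TP2 and TP3 risk periods can run to last dose + 35 while the Observation risk period starts at last dose + 1, so those days would otherwise count twice.
5. Replace the term incidence rates in Protocol 9.4.3 and SAP section 9 wherever only percentages are shown.
6. Reconcile the Protocol's whole-study summary for the initial active group with SAP section 8, either by adding the column or by removing the commitment.

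The cost is a few extra table columns and one footnote stating the constant-hazard assumption and the limited person-time. The risk-period dates are already defined in the SAP and no new data are needed.
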